##### 4.4.2.2. Post-Operative Analysis

The post-operative secondary analyses for this study will be to compare the final measured post-operative FEV1 value (spirometry) to those predicted by both hyperpolarized  $^{129}\text{Xe}$  MRI and  $^{133}\text{Xe}$  scintigraphy.

The calculation of predicted post-operative FEV1 will be based on pre-operative imaging and the extent of planned lung resection. The scans will be quantified using commercially available software to report the fraction of activity arising from each of 6 lung zones, 3 in each lung. On the eCRF, the surgeon will check the zones that are planned for resection. The predicted post-operative FEV1 will be calculated by multiplying the percentage of function remaining in the non-operated zones by the pre-operative FEV1. For example, assume that the quantified fractions of activity for zone 1 to zone 6 are 15%, 20%, 25%, 10%, 15% and 15%, respectively and the surgeon notes that zone 4 and zone 5 are planned for complete resection. Then, the predicted post-operative FEV1 = pre-operative FEV1 \*  $\{(15\%+20\%+25\%) + (15\%)\}$ .

For each of these two comparisons, the null hypothesis that the mean difference is equal to zero, will be tested using the one-sample t test. The two-sided 95% CI for the mean difference will also be reported. A third comparison will be to test the null hypothesis that the mean difference between predicted post-operative FEV1 (measured in L) predicted by hyperpolarized  $^{129}\text{Xe}$  MRI and  $^{133}\text{Xe}$  scintigraphy is equal to zero. This analysis will also be conducted using the one-sample t test and the two-sided 95% CI for the mean difference will be reported.

This analysis will use the Post-operative Analysis Set. Because the final post-operative FEV1 value will be obtained approximately 3 months after surgery, this post-operative secondary analysis will be performed about 3 months after the other planned statistical analyses.

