### 4. STATISTICAL METHODS

All final statistical analyses will be performed by the sponsor or designee after the study is completed and the database is locked and released.

All descriptive statistics for continuous variables will be reported using the number of observations (n), mean (arithmetic unless otherwise specified), standard deviation (SD), median, minimum and maximum. Categorical variables will be summarized as the number and percentage of subjects.

All inferential statistics will be based on the 5% level of significance (two-sided).

All data from this study will be presented in listings. All listings will be sorted by treatment sequence, subject number, and visit date, as applicable.

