### 9.4. Secondary Efficacy Analyses

The post-operative secondary analysis was revised to provide a comparison between the measured post-operative FEV1 and each scan-predicted post-operative FEV1. An additional

analysis was added to compare the difference between predicted post-operative FEV1 from each scan.

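### The post-operative analysis checks each scan against measured FEV1 only through its mean signed error, so the size of the individual prediction errors is never compared

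*SAP*

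**What the plan says.** SAP 4.4.2.2 (Post-Operative Analysis) sets measured post-operative FEV1 against the prediction from each scan. For these two comparisons, "the null hypothesis that the mean difference is equal to zero, will be tested using the one-sample t test". On intervals it says: "The two-sided 95% CI for the mean difference will also be reported".

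It then turns to the two predictions themselves: "A third comparison will be to test the null hypothesis that the mean difference between predicted post-operative FEV1 (measured in L) predicted by hyperpolarized". The rest of that sentence names the two scans and a null value of zero, and the method is again a one-sample t test with a 95% CI. On the population: "This analysis will use the Post-operative Analysis Set". That set consists of efficacy subjects who also have a post-operative spirometry value. Neither document plans its size.

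SAP Section 4 sets a two-sided 5% level and makes n, mean, SD, median, minimum and maximum the standard summary of continuous variables, with all data listed. SAP 4.5.1 and 4.5.2 look at standardised and patient-level differences, but of one scan from the other. SAP 9.4 records that the post-operative analysis was revised from the protocol. Protocol 8.7 had used an equivalence test with the primary margin, also on the mean difference.

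**The concern.** Measured post-operative FEV1 is the only outcome in the trial against which either scan's prediction can be checked. Whether a prediction is useful for an individual patient depends on how far it falls from the value later measured, and a mean signed error does not describe that. A scan that is 0.4 L too high in half the patients and 0.4 L too low in the other half has a mean error of zero.

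The test of zero also responds to spread in an unhelpful direction. For a given bias, a noisier scan has a wider interval and is less likely to be declared different from zero. A reader who takes non-significance for both scans as evidence that both predict well, or equally well, would be relying on a result that says little about individual error.

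Restoring the protocol's margin would not cure this. A margin on the mean still lets errors cancel.

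**Working it through.** **The plan's own figure.** The only computed figure is the sample size in SAP Section 2: 15 subjects at 0.21 L and 32 at 0.32 L, margin 0.3 L, 90% power. Exact power for a 95% CI inside ±0.3 L, with true difference zero, is 90.55% at n = 15 and 90.54% at n = 32 if the quoted values are per-method SDs (SD of the difference = √2 × 0.21 = 0.297 L and √2 × 0.32 = 0.453 L). So the stated sizes reproduce on that reading. They concern predicted FEV1 from scan against scan. The post-operative analysis has no stated sample size or power.

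**What each comparison estimates.** Let M be measured post-operative FEV1, P129 and P133 the predictions, and define errors e129 = P129 − M and e133 = P133 − M.

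- First comparison: mean(e129). Second: mean(e133). Both are bias estimates.
- Third: for every subject, (P129 − M) − (P133 − M) = P129 − P133. M cancels. The point estimate is the first minus the second. Its CI is not redundant, because it depends on the correlation of the two errors, which the first two CIs do not give.

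**What can be recovered.** From a CI and n, SD = half-width × √n / t, and root mean squared error = √(mean² + SD² × (n − 1)/n). At n = 20, t(19, 0.975) = 2.093, so an SD of 0.40 L gives a half-width of about 2.093 × 0.40/√20 = 0.19 L, and 0.10 L gives about 0.05 L. Spread is therefore visible scan by scan, but there is no paired comparison of error size.

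**Simulations (20,000 or more trials per setting, normal errors).** The number operated, SDs, biases and correlations below are all assumptions.

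1. *Both scans unbiased, independent errors, n = 20.*
   - SD 0.40 vs 0.20 L (mean absolute error 0.32 vs 0.16 L): all three planned tests are non-significant in 89% of trials. A paired t test on absolute error rejects in 74%.
   - SD 0.40 vs 0.10 L (0.32 vs 0.08 L): 89% and 99.8%.
2. *A precise but slightly biased scan against a noisy unbiased one, n = 20.* Bias 0.1 L with SD 0.1 L (mean absolute error 0.12 L) against bias 0 with SD 0.4 L (0.32 L). The planned test rejects the scan with the smaller errors in 99% of trials and the one with the larger errors in 5%.
3. *Opposite biases, n = 20.* +0.15 and −0.15 L, SD 0.17 L each. Error size is equal, yet the third comparison rejects in over 99% of trials; the paired absolute-error test rejects in 5%. The third comparison is correctly detecting disagreement, which is a different question from error size.
4. *Shared error.* Both predictions use the same pre-operative FEV1 and planned zones and are compared with the same M, so part of the error is common. Scan-specific SDs are 0.20 vs 0.10 L. Total SD = √(shared² + specific²).

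| Shared SD (L) | Total SDs (L) | Paired absolute-error test rejects: n = 10 | n = 20 | n = 32 |
|--|--|--|--|--|
| 0.20 | 0.28 vs 0.22 | about 11% | 20% | 31% |
| 0.30 | 0.36 vs 0.32 | about 8% | 12% | 17% |

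Correlation alone does not reduce power. With total SDs fixed at 0.17 vs 0.34 L, raising the correlation from 0 to 0.6 raises rejection at n = 20 from 73% to 87%. The loss in the table comes from the shared part pulling the two total SDs together.

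**The case against.** The strongest reply is that ranking the scans by accuracy is not an objective. The secondary objective in Protocol 2.2 and SAP 1.1.2 is equivalence of the FEV1 values predicted by the two scans, and the third comparison addresses that pair directly. This stands. The third comparison belongs in the plan, and whether a test of zero suits an equivalence objective is a separate question.

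Three stronger readings are tempting, and the documents do not support them.

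- *The trial cannot say which scan predicts better.* The data are collected and listed, SD is a standard summary, and each scan's error SD follows from its CI and n. What is missing is a pre-specified comparison of error size.
- *The third comparison adds nothing.* Its point estimate follows from the first two, but its interval does not.
- *The SAP presents the third comparison as an accuracy test.* Neither 4.4.2.2 nor 9.4 calls it that.

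It is also fair to say that a paired absolute-error test may have little power, as the shared-error results show, and that without a margin it could not establish that 129Xe is no worse. Both points limit how the added estimate should be presented. They do not make the mean signed error a measure of individual accuracy.

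**Conclusion.** The point holds in a limited form. SAP 4.4.2.2 assesses each scan against measured post-operative FEV1 only by mean signed error, and no other planned analysis compares error size with the measured outcome. The mean-zero tests can favour the scan with the larger errors, as the 99% against 5% example shows.

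How much an absolute-error comparison would add is uncertain, because the documents give neither the number operated nor the error structure. At n = 20 the paired test rejects in 74% of trials under independent SDs of 0.40 and 0.20 L, and in about 12-20% under the shared-error assumptions. The estimate and its CI therefore matter more than a p-value. This is an inexpensive improvement to a secondary analysis; the primary conclusion does not depend on it.

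**What to change.** In SAP 4.4.2.2, for the Post-operative Analysis Set, add:

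- for each scan, the mean absolute error |predicted − measured| with a 95% CI, and limits of agreement against measured FEV1;
- the paired mean difference in absolute error, 129Xe minus 133Xe, with a two-sided 95% CI.

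State that these are supportive estimates and not a test of no worse, since no margin is set. Keep the two signed means and label them bias estimates. Keep the third comparison and label it agreement between the scans.

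The cost is a few lines of SAP text and one table from data already collected. The downside is one more secondary estimate, which may be imprecise if few subjects are operated.

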## 8.2. Analysis Populations

This study will evaluate 2 different subject populations:

- **Efficacy Population:** The efficacy analysis set will consist of all subjects that have both a  $^{129}\text{Xe}$  MRI scan and a  $^{133}\text{Xe}$  scintigraphy scan. Primary and the 6-zone analysis secondary efficacy endpoints will be analyzed using the efficacy analysis set.
- **Post-operative Population:** This analysis set will consist of all subjects that have both a  $^{129}\text{Xe}$  MRI scan and a  $^{133}\text{Xe}$  scintigraphy scan, and have a post-operative FEV1 (spirometry) value.
- **Safety:** The safety analysis set will consist of all subjects who received at least 1 dose of either hyperpolarized  $^{129}\text{Xe}$  or  $^{133}\text{Xe}$ . Secondary safety endpoints will be analyzed using the Safety analysis set.

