### 8.6. Primary Efficacy Analysis

The primary analysis for this study will be to test the mean difference in predicted post-operative FEV1 (measured in L/sec) values as measured using hyperpolarized  $^{129}\text{Xe}$  gas MRI relative to  $^{133}\text{Xe}$  scintigraphy (reference standard). The primary analysis will be conducted by estimating the 95% confidence interval (CI) for the mean difference in predicted FEV1 from the 2 methods. The scans will be quantified using commercially available software to report the fraction of activity arising from 6 zones. This will be used to predict post-operative FEV1 by multiplying the percentage of function remaining in the non-operated zones by pre-operative FEV1. The CI will be constructed assuming that the within-subject difference between methods is normally distributed. If the 95% CI for the mean difference is contained within the interval (-0.30, +0.30 L/sec), equivalence will have been demonstrated.

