### 8.7. Secondary Efficacy Analysis

The post-operative secondary analysis for this study will be to test the mean difference in predicted post-operative FEV1 (measured in L/sec) values as measured using hyperpolarized  $^{129}\text{Xe}$  gas MRI and  $^{133}\text{Xe}$  scintigraphy (reference standard) relative to the final post-operative FEV1 value (spirometry). The secondary equivalence analysis will be conducted using the same methodology and same equivalence margin as specified for the primary analysis.

The 6-zone secondary analysis for this study will be to evaluate the individual percentage function assessments from each of the 6 zone analyses from both the  $^{129}\text{Xe}$  and the  $^{133}\text{Xe}$  ventilation images. The equivalence margin will be 5 percentage points. Thus, for each of the six zones, equivalence will have been demonstrated if the 95% CI for the mean difference is contained within the interval (-5%, +5%).

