#### 1.1.2. Secondary Objective

The secondary objectives of this study are to:

- Assess the safety and tolerability of hyperpolarized  $^{129}\text{Xe}$  gas;
- Evaluate regional ventilation defects in each of the 6 zones, and
- Demonstrate the equivalence of post-operative forced expiratory volume in 1 second (FEV1) values predicted using hyperpolarized  $^{129}\text{Xe}$  as compared to  $^{133}\text{Xe}$  scintigraphy.

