## 2. DETERMINATION OF SAMPLE SIZE

The sample size required to demonstrate equivalence is driven by 2 factors: 1) the intra-subject variability of the difference between the predicted post-operative FEV1 from the 2 methods, and 2) the pre-specified equivalence margin. From prior literature, the intra-subject variability for  $^{133}\text{Xe}$  scintigraphy leads to an estimated variability in predicted post-operative FEV1 of 0.21 L. Similarly, prior studies have suggested that the equivalence margin between the 2 imaging techniques currently used for resection planning is 0.3 L. Using these assumptions, and based on

the use of a two-sided test at the  $\alpha = 0.05$  level of significance, a sample size of 15 subjects is required for 90% power. However, given limited literature on  $^{133}\text{Xe}$  variability, we have accounted for the possibility that it could be higher. If true variability is 0.32 L, then a sample size of 32 subjects will provide 90% power to establish equivalence.

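### The SAP keeps an equivalence objective for scan-predicted post-operative FEV1 but tests it only against zero difference, with no margin, and limits the scan-versus-scan comparison to operated subjects

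*SAP*

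**What the plan says.** **Objective.** SAP 1.1.2 repeats the protocol's secondary objective: "Demonstrate the equivalence of post-operative forced expiratory volume in 1 second (FEV1) values predicted using hyperpolarized" 129Xe as compared with 133Xe scintigraphy.

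**Protocol analysis.** Scan-versus-scan predicted FEV1 was the primary endpoint. Protocol 8.6 gave its decision rule: "If the 95% CI for the mean difference is contained within the interval (-0.30, +0.30 L/sec), equivalence will have been demonstrated". Protocol 8.2 set its population as all subjects with both scans: "Primary and the 6-zone analysis secondary efficacy endpoints will be analyzed using the efficacy analysis set". For predicted versus measured post-operative FEV1, Protocol 8.7 states: "The secondary equivalence analysis will be conducted using the same methodology and same equivalence margin as specified for the primary analysis".

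**SAP analysis.** SAP 4.1.1 and 4.4.1 move the primary endpoint to the proportion of remaining function, with a margin of ±14.7%. FEV1 is then analysed only in SAP 4.4.2.2. For each scan's prediction against measured FEV1, "the null hypothesis that the mean difference is equal to zero, will be tested using the one-sample t test". The scan-versus-scan comparison follows: "A third comparison will be to test the null hypothesis that the mean difference between predicted post-operative FEV1" from the two scans is zero, again by one-sample t test. Two-sided 95% CIs are reported for all three, with no limits attached. On population: "This analysis will use the Post-operative Analysis Set". SAP 4.2.1 restricts that set to Efficacy Analysis Set members who also have a post-operative spirometry value.

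**Record of the change.** SAP 9.4 says the post-operative analysis was revised to compare measured FEV1 with each prediction, and that a comparison of the two predictions was added. It does not say that the equivalence rule was removed.

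**The concern.** The objective and the analysis ask different questions. Failing to reject zero difference may only reflect a small sample. Rejecting it may only reflect a precise estimate of a trivial difference. Neither result is evidence for or against equivalence within a stated limit.

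Elsewhere the SAP writes the rule out where it wants an equivalence conclusion: SAP 4.4.1 (±14.7%) and SAP 4.4.2.1 (±5 percentage points per zone) both require the 95% CI to lie inside the margin. The FEV1 objective has no such sentence, so any equivalence statement about predicted FEV1 would rest on a rule chosen outside the SAP's analysis section.

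The population is a second problem. Comparing the two predictions requires both scans, the zones planned for resection and pre-operative FEV1. Protocol 6.7 and the Schedule of Events place spirometry before imaging for every subject. Post-operative spirometry does not enter this comparison, yet subjects without it are excluded. Only the two predicted-versus-measured comparisons need the smaller set.

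**Working it through.** **Inputs**

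- Margin 0.30 L: Protocol 8.6 (printed as L/sec); SAP 2 and 3 (in L).
- Variability 0.21 L (base) and 0.32 L (contingency), 90% power, n = 15 and n = 32: SAP 2.
- Two-sided 5% level, i.e. a 95% CI: SAP 4.
- Mean pre-operative FEV1 2.02 L, used to convert the margin: SAP 3.
- Size of the operated subset: not given. Assumed here: n = 10, 16 and 24.

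**Step 1. Reproduce the plan's sample size.** The rule is that d̄ ± t(n−1, 0.975) × SD/√n lies within ±0.30 L. Power is computed at a true difference of zero, integrating over the chi-square distribution of the sample variance.

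- Taking 0.21 and 0.32 as the SD of the within-subject difference, the smallest n for 90% power is 9 and 17. This does not match.
- Taking them as per-scan SDs, the difference SD is √2 × 0.21 = 0.297 L and √2 × 0.32 = 0.4525 L. The smallest n is 15 (90.6%) and 32 (90.5%). Both match.

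The √2 step is inferred, because the documents do not say that the figures are per scan. The stated sample sizes are therefore those of a ±0.30 L equivalence test on predicted FEV1, which the SAP no longer contains.

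**Step 2. Behaviour of the planned zero-difference test** (non-central t, two-sided 5%).

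- True difference 0.30 L, at the margin, with difference SD 0.4525 L: the test is non-significant with probability 54% at n = 10, 30% at n = 16 and 12.5% at n = 24. A CI-within-margin rule would wrongly declare equivalence at most 2.5% of the time.
- True difference 0.10 L, well inside the margin, at n = 32: the test is significant 23% of the time at SD 0.4525 L and 46% at SD 0.297 L.

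**Step 3. Cost of the subset, if the ±0.30 L rule were applied to it.**

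| n | Power, SD 0.297 L | CI half-width | Power, SD 0.4525 L | CI half-width |
|---|---|---|---|---|
| 10 (assumed) | 63% | 0.21 L | 12% | 0.32 L |
| 16 (assumed) | 93% | 0.16 L | 41% | 0.24 L |
| 24 (assumed) | 99.4% | 0.13 L | 75% | 0.19 L |
| 32 (planned completers) | over 99.9% | 0.11 L | 90.5% | 0.16 L |

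Half-width is t(n−1, 0.975) × SD/√n. For n = 16 and SD 0.4525 L: 2.131 × 0.4525/4 = 0.24 L.

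These figures are for scan versus scan. The documents give no SD for predicted versus measured FEV1, so no power can be quoted for those two comparisons.

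**Step 4. Does the primary test settle the litre-scale objective?** The margin of 14.7% in litres is 0.147 × pre-operative FEV1:

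- at 2.02 L: 0.297 L;
- at 1.5 L (assumed): 0.22 L;
- at 3.0 L (assumed): 0.44 L.

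The two margins agree only near 2.02 L. Equivalence of the mean proportion does not by itself give equivalence of the mean FEV1 in litres.

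**The case against.** The strongest reply is that the change was deliberate. The SAP version log lists the revision of this analysis among those made after discussion with FDA. SAP 9.2 explains that baseline FEV1 was taken out of the primary endpoint because it may add unnecessary variability. On that view the sponsor moved FEV1 to estimation and left a stale objective behind, and a ±0.30 L test on the full set would bring back the superseded primary. This explains why the primary changed. It gives no reason for dropping a decision rule from an objective that SAP 1.1.2 still states. Deleting or rewording the objective would remove the contradiction, but the SAP has not done that.

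Second, the margin has not vanished. SAP 2 still says that "prior studies have suggested that the equivalence margin between the 2 imaging techniques currently used for resection planning is 0.3 L", SAP 3 repeats it, and a 95% CI is planned for each comparison, so a reader could set one against the other. True, but no rule tells anyone to do so.

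Third, using one set keeps the three comparisons on the same subjects, and for unoperated subjects the resection is only potential. That is a reasonable motive for also showing the scan-versus-scan result in the operated subset. It does not justify showing it only there, since the primary analysis already uses planned zones for everyone.

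Fourth, the loss of precision may be small. SAP 3 also gives a variability of 0.17 L in pneumonectomy patients. With the same √2 step the difference SD is 0.240 L, and power is 88%, 99.3% and over 99.9% at n = 10, 16 and 24. This stands: the cost of the subset depends on its unknown size and on the SD. The missing decision rule does not depend on either.

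**Conclusion.** The concern holds. Followed exactly, the SAP cannot reach a conclusion on its stated objective of equivalence in predicted post-operative FEV1, because no FEV1 analysis carries a margin. This follows from the text and needs no numerical assumption. Restricting the scan-versus-scan comparison to operated subjects is unnecessary. Its cost ranges from negligible (24 operated subjects, difference SD 0.297 L or less) to severe (10 operated subjects, 0.4525 L: 12% power against 90.5% at n = 32). That range rests on assumed subset sizes and on the √2 reading, which reproduces both of the plan's sample sizes. The primary equivalence test and the by-zone analysis are not affected. This should be fixed before database lock, but it does not threaten the main result.

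**What to change.** In SAP 4.4.2.2:

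1. Run the 129Xe- versus 133Xe-predicted FEV1 comparison on the Efficacy Analysis Set, and declare equivalence if the two-sided 95% CI for the mean difference lies within (−0.30, +0.30 L). A repeat on the Post-operative Analysis Set can be shown as supportive.
2. Keep the Post-operative Analysis Set for the two predicted-versus-measured comparisons. For these, either restore the Protocol 8.7 equivalence rule and justify the margin, or label them as estimation with 95% CIs and state that they are not evidence of equivalence. The documents support 0.3 L only as a margin between imaging techniques, not between a prediction and a measured value.
3. Record in SAP 9.4 what was changed from Protocol 8.6 and 8.7, and why.

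The cost is SAP wording and one additional full-set output, with the review, approval and submission to FDA before database lock that SAP 1 requires. No new data are needed: the scans, planned zones and pre-imaging spirometry are already scheduled for every subject.
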